## 4.4.1. Analysis of Serum-Binding Antibody (IgG)

If more than 10% of participants are eliminated from any of the PPS in any treatment group, a sensitivity analysis will be carried out using the Exposed Set.

4.4.1.1. GMCs and GMR from baseline of binding IgG Ab against SARS-CoV-2 Spike WT (D614), SARS-CoV-2 Spike BA.5, SARS-CoV-2 Spike D614G, SARS-CoV-2 Spike (B.1.617.2, AY.4), SARS-CoV-2 Spike (B.1.1.529, BA.1, BA.1.15), SARS-CoV-2 Spike BQ.1, SARS-CoV-2 Spike XBB.1, SARS-CoV-2 Spike BA.2.275, SARS-CoV-2 Spike XBB.1.5, SARS-CoV-2 Spike XBB.1.16 variants at each collection timepoint

The descriptive summary will consist in the number of results available (N), standard deviation, median, interquartile, minimum, and maximum, GMC/GMR, and associated 95% CIs.

Immunogenicity of the study vaccine will be assessed through GMCs with associated CI at each collection time point before the vaccination (Day 1) and after the vaccination (Day 15, Day 31, M6). Likewise GMRs from baseline, percentage above Lower Limit of Quantitation (LLOQ), and corresponding 95% CI will be reported. The corresponding bar charts for GMC and GMR will be provided in log scale (log10 will be used for GMC while log2 will be used for GMR). For these analyses, CI for GMC and GMR will be derived from a student distribution assuming that log-transformed concentration is normally distributed with variance specific to each treatment group.

Distribution of geometric mean concentration fold changes from baseline for at least 2, 4, and 8 folds, with their exact 95% CI will be tabulated, by study group and visit.

The GMC at each post dose time point, the GMR from baseline, and the 95% CIs in all treatment groups will also be analysed using an ANCOVA model on log10 transformed concentrations with treatment group as fixed in the model, and log10 transformed Day 1 baseline value as covariable.

Once Part B data are available, Part A and Part B data will be pooled together for model based analyses. When pooled, the study part will be added as a fixed factor and adjusted GMC or GMR from baseline will be estimated under Part A condition. Groups common in Part A and Part B will be combined as one group respectively for the pooled analysis. Output will be displayed by 3  $\mu$ g, 10  $\mu$ g, 30  $\mu$ g, 100  $\mu$ g, and pooled placebo.

4.4.1.2. Seroresponse rates, based on binding IgG Ab concentrations against SARS-CoV-2 Spike WT (D614), SARS-CoV-2 Spike BA.5, SARS-CoV-2 Spike D614G, SARS-CoV-2 Spike (B.1.617.2, AY.4), SARS-CoV-2 Spike (B.1.1.529, BA.1, BA.1.15), SARS-CoV-2 Spike BQ.1, SARS-CoV-2 Spike XBB.1, SARS-CoV-2 Spike BA.2.275, SARS-CoV-2 Spike XBB.1.5, SARS-CoV-2 Spike XBB.1.16 variants.

IgG seroresponse rate is defined as the percentage of participants who have either a baseline concentration < LLOQ and a post-dose concentration  $\ge$ 4\*LLOQ or a baseline concentration  $\ge$ LLOQ and at least a 4-fold increase from baseline to post-dose concentration.

The percentage of participants with IgG seroresponse of serum SARS-CoV-2 Spike WT, SARS-CoV-2 Spike BA.5, SARS-CoV-2 Spike D614G, SARS-CoV-2 Spike (B.1.617.2, AY.4), SARS-CoV-2 Spike (B.1.1.529, BA.1, BA.1.15), SARS-CoV-2 Spike BQ.1, SARS-CoV-2 Spike XBB.1, SARS-CoV-2 Spike BA.2.275, SARS-CoV-2 Spike XBB.1.5, SARS-CoV-2 Spike XBB.1.16 variants specific binding IgG from baseline at day 15, Day 31, M6 will be tabulated by study group with 2-sided 95% exact CIs.

## 4.4.2. Analysis of Cell-Mediated Immune Response

CMI Analysis will be performed using the Intracellular Cytokine Staining assay for WT(D614) and BA5 variants.

Descriptive statistics at each timepoint (Day 1, Day 15, Day 31, and M6) and change from baseline will be provided by treatment group for:

- SARS-COV-2 spike-specific polypositive CD4+ T cell responses (frequency per million CD4) expressing at least 2 different markers with at least one cytokine, among CD40 Ligand (CD40L), 41-BB, IL-2, TNF- α, IFN- γ, IL-13 and IL-17 upon in vitro stimulation
- SARS-COV-2 spike-specific polypositive CD8+ T cell responses (frequency per million CD8) expressing at least 2 different markers with at least one cytokine, among CD40 Ligand (CD40L), 41-BB, IL-2, TNF- α, IFN- γ, IL-13 and IL-17 upon in vitro stimulation.

Descriptive statistics of

- 1. CD4 T helper profile expressing at least IFN-  $\gamma$  (Th1);
- 2. CD4 T helper profile expressing at least IL-13 (Th2);
- 3. CD4 T helper profile expressing at least IL-17 (Th17)

at each timepoint (Day 1, Day 15, Day 31, and M6) will be provided by treatment group. The descriptive summary will consist in the number of results available (N), standard deviation, median, interquartile, minimum, and maximum, GMF and associated 95% CIs. The 95% CI will be calculated based on the t-distribution of the log-transformed values, then back-transformed to the original scale for presentation.

For polypositive CD4+ T cell and CD8+ T cell frequencies, geometric mean of frequency fold rise from baseline (GMFR) with 95% CI as well as the frequency of cells above LLOQ will also be provided. For the GMF and GMFR computation, titer below the LLOQ will be assigned the LLOQ value.

Bar Charts of each cell-mediated response for cytokines by treatment group and timepoint will also be produced on log10 transformed scale for GMF and log2 transformed scale for GMFR, including fold rise from baseline for polypositive CD4+ T cell and CD8+ T cell frequencies.

Supporting listing of CMI parameters will be sorted by treatment group and participant number.

As the frequency of CD4 (or CD8) by in vitro stimulation is separated for different antigen peptides or spikes, the frequency of antigen specific CD4 (or CD8) T cells for each individual participant will be calculated as follows:

1. For each antigen peptides or spikes, the difference between the frequency of CD4 (or CD8), upon in vitro stimulation with the antigen peptides or spikes (induction condition), and the frequency of CD4 (or CD8), upon in vitro stimulation in medium only (background condition) will be computed. Differences less or equal to one (1)

per  $10^6$  CD4 (or CD8) T cells will be imputed to 1 antigen specific CD4 (or CD8) T cell per  $10^6$  CD4 (or CD8) T cells.

- 2. The frequency associated to an antigen will then be obtained by summing the frequency of associated peptides or spikes as applicable:
  - for Wuhan antigen, S1 WU and S2 WU-SA frequencies will be added.
  - for Omicron, P1 Omicron and P2 Omicron frequencies will be added.

The imputation to LLOQ will be done on the frequency sum.

## 4.4.3. Incidence of confirmed symptomatic and asymptomatic SARS-CoV-2 infection

The percentage of participants of laboratory-confirmed SARS-CoV-2 by N protein seroconversion at either (D15, D31, and M6) or RT-PCR at either (D8, D15) will be summarized by treatment.

Percentage of laboratory-confirmed (RT-PCR) SARS-CoV-2 infection reported as AESI post-vaccination will be summarized by treatment.

Percentage of laboratory-confirmed (RT-PCR) SARS-CoV-2 infection reported as AESI or SARS-CoV-2 detected by N-protein and R-PCR post-vaccination will be summarized by treatment.

## 4.4.4. Other Tertiary Endpoints

Genetic sequence of SARS-CoV-2 variant S protein in confirmed (RT-PCR) SARS-CoV-2 positive participants will not be reported.

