### Table 3 Study objectives, endpoints and estimands

Objective(s)		Endpoints/Estimands
•	To describe cell-mediated immune responses induced by the mRNA-CR-04 vaccine up to study conclusion.	
 
Frequency of CD4+/CD8+ T-cells specific for S protein encoded by the vaccine SARS-CoV-2 and WT strains measured by intracellular cytokine staining assay at each time point (D1, D15, D31, M6).
 
Cellular immune responses including, but not limited to Th1 and Th2 profiles as determined by flow cytometry using ICS at each time point (D1, D15, D31, M6).
 

•	To describe the incidence of confirmed symptomatic and asymptomatic SARS-CoV-2 infection.	
 
Percentage of laboratory-confirmed (N protein seroconversion) asymptomatic SARS-CoV-2 infection at each time point (D1, D15, D31, M6).
 
Percentage of laboratory-confirmed (RT-PCR) symptomatic SARS-CoV-2 infection at screening, D1, D8, D15, as well as at unscheduled visits.
 

•	To evaluate the genetic sequence of SARS-CoV-2 variant S protein in confirmed (RT-PCR) SARS-CoV-2 positive participants.	
 
Comparison of SARS-CoV-2 S protein genetic sequence of viral isolates (when available) to the vaccine mRNA sequence
 
Identification of SARS-CoV-2 variants.
 

•	To further characterize the humoral response (including, but not limited to functionality of antibodies) and cellular response, specific for the vaccine encoded SARS-CoV-2, WT and other relevant strains.	
 
S-specific responses at D1, D15, D31, M6
 
Other read-outs may be performed if deemed necessary.
 

Ab: Antibody; AE: Adverse event; AESI: Adverse events of special interest; D: Day; GMR: Geometric mean ratio; GMT: Geometric mean titer; ICS: intracellular cytokine staining; IgG: Immunoglobulin G; M: Month; MAAE: Medically attended adverse events; N: Nucleocapsid; pIMD: potential Immune-mediated disease; RT-PCR: Real-time polymerase chain reaction; S: Spike; SAE: Serious adverse event; VAED: Vaccine associated enhanced disease; WT: Wild type.

\*AESI include pIMDs, myocarditis/pericarditis, virologically confirmed COVID-19 cases and anaphylaxis or severe hypersensitivity within 24 hours after study vaccination (Section 8.4.4).

Details related to attributes of estimands covering intercurrent events and strategies, population, treatment condition, and population level summary will be provided in SAP.

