#### 8.2.2. Laboratory assays

Following laboratory assays will be performed (Table 10).

- PCR assay will be used to detect SARS-CoV-2 infection. If the sample is positive and sufficient material is available, sequencing of the SARS-CoV-2 isolate will be performed by genomic RNASeq.
- Serological assay to monitor the asymptomatic infection will be performed using an ECL to measure serum-binding Abs IgG levels specific for N protein of SARS-CoV-2.
- The vaccine-induced humoral immunity will be evaluated using serological assays determining the capacity of the serum of SARS-CoV-2 vaccinated participants to neutralize pseudoviruses bearing S protein from vaccine encoded SARS-COV-2 and from the WT (D614G).
- Further characterization of the humoral immune response will be performed using ECL for measurement of IgG antibodies binding to the SARS-CoV-2 S protein (at least vaccine encoded SARS-CoV-2 variant and WT).
- The cell-mediated immunity will be evaluated by assessing the frequency of SARS-CoV-2 S-specific CD4+ and CD8+ T-cells expressing specific activation or immune markers using ICS per million of total CD4+ or CD8+ T-cells respectively.

Assay Type	System	Component	Challenge	Method	Laboratory**
Humoral immunity (antibody determination)*	Serum	Anti-S binding IgG Ab	ti-S binding IgG Ab		PPD
	Serum	Anti-SARS-CoV-2 neutralizing titer	NA	Pseudo Neutralization assay	Nexelis
Cell-mediated immunity	PBMCs	CD4+/CD8+ T-cells expressing IL- 2/IFNy/TNFa/IL- 13/IL-17/4- 1BB/CD40L	Peptide pools covering the SARS-CoV-2 S protein	ICS	GSK
Detection of SARS- CoV-2 Infection	Serum	Anti-N IgG Ab	NA	ECL	PPD
Detection of SARS- CoV-2 Infection	Nasopharyngeal Swab	SARS-CoV-2 RNA	NA	RT-PCR	PPD
Sequencing of SARS-CoV-2 Isolates	Nasopharyngeal Swab	SARS-CoV-2 RNA	NA	RNASeq	PPD

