# 9.4.3. Analyses of exploratory immunogenicity endpoints

Additional exploratory immunological assays evaluating S-specific or disease-related antigen specific humoral or cellular immune responses, including but not limited to antibody functionality (Fc $\gamma$  R binding capacity, IgG affinity), isotype titer and isotype avidity, deep immunophenotyping of cellular responses might also be performed. The analyses will be performed separately for study Part A and Part B participants. In addition, pooled analyses where groups common in Part A and Part B are combined as one group respectively will be performed. Appropriate pooled analyses, such as the ANCOVA planned on neutralizing antibody titers will also be performed on the IgG antibody responses.

Analysis of tertiary endpoints detailed in Section 3 will be described in the SAP.

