• To describe cell-mediated immune responses induced by the mRNA-CR-04 vaccine up to study conclusion.	
 
Frequency of CD4+/CD8+ T-cells specific for S protein encoded by the vaccine SARS-CoV-2 and WT strains measured by intracellular cytokine staining assay at each time point (D1, D15, D31, M6).
 
Cellular immune responses including, but not limited to Th1 and Th2 profiles as determined by flow cytometry using ICS at each time point (D1, D15, D31, M6).
 

• To describe the incidence of confirmed symptomatic and asymptomatic SARS- CoV-2 infection.	
 
Percentage of laboratory-confirmed (N protein seroconversion) asymptomatic SARS-CoV-2 infection at each time point (D1, D15, D31, M6).
 
Percentage of laboratory-confirmed (RT-PCR) symptomatic SARS-CoV-2 infection at D8, D15, as well as at unscheduled visits.
 

• To evaluate the genetic sequence of SARS-CoV-2 variant S protein in confirmed (RT-PCR) SARS-CoV-2 positive participants.	
 
Comparison of SARS-CoV-2 S protein genetic sequence of viral isolates (when available) to the vaccine mRNA sequence
 
Identification of SARS-CoV-2 variants.
 

• To further characterize the humoral response (including, but not limited to functionality of antibodies) and cellular response, specific for the vaccine encoded SARS-CoV-2, WT and other relevant strains.	
 
S-specific responses at D1, D15, D31, M6
 
Other read-outs may be performed if deemed necessary.
 

Ab: Antibody; AE: Adverse event; AESI: Adverse events of special interest; D: Day; GMR: Geometric mean ratio; GMT: Geometric mean titer; ICS: intracellular cytokine staining; IgG: Immunoglobulin G; M: Month; MAAE: Medically attended adverse events; N: Nucleocapsid; pIMD: potential Immune-mediated disease; RT-PCR: Real-time polymerase chain reaction; S: Spike; SAE: Serious adverse event; VAED: Vaccine associated enhanced disease; WT: Wild type.

\*AESI include pIMDs, myocarditis/pericarditis, virologically confirmed COVID-19 cases and anaphylaxis or severe hypersensitivity within 24 hours after study vaccination (Protocol Section 8.4.4).

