## 4.9. Changes to Protocol Defined Analyses

Because RT-PCR at screening and Day 1 do not contribute to the incidence of SARS-CoV-2 infection they have been removed from the SARS-CoV-2 infection endpoint and summary.

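### SAP 4.4.4 rules out reporting the spike-sequence data that a tertiary objective in both documents calls for, and SAP 4.9 does not record the departure

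*SAP*

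**What the plan says.** The protocol's tertiary objective (section 3, Table 3) reads "To evaluate the genetic sequence of SARS-CoV-2 variant S protein in confirmed (RT-PCR) SARS-CoV-2 positive participants". Its two endpoints are "Comparison of SARS-CoV-2 S protein genetic sequence of viral isolates (when available) to the vaccine mRNA sequence" and the identification of variants. SAP Table 1 (section 1.1) repeats the objective and both endpoints, including "Identification of SARS-CoV-2 variants".

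On data collection, protocol 8.2.2 states: "If the sample is positive and sufficient material is available, sequencing of the SARS-CoV-2 isolate will be performed by genomic RNASeq". Protocol 8.4.4.2.2 adds that any available genotyping results from outside testing will be requested.

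On analysis, protocol 9.4.3 states: "Analysis of tertiary endpoints detailed in Section 3 will be described in the SAP". The only text in the SAP on what will be done with the sequence data is section 4.4.4: "Genetic sequence of SARS-CoV-2 variant S protein in confirmed (RT-PCR) SARS-CoV-2 positive participants will not be reported".

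SAP 4.9, the section for changes to protocol-defined analyses, contains one entry: "Because RT-PCR at screening and Day 1 do not contribute to the incidence of SARS-CoV-2 infection they have been removed" from the infection endpoint and its summary. Sequence reporting is not mentioned there.

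**The concern.** A stated objective, a laboratory step that serves it, and a refusal to report the result stand together in the current documents with no explanation. Someone comparing the study report with the protocol would find an objective with no result, and nothing in the plan to say whether that was decided, why, or where the data went.

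The scientific stake is modest but real. The vaccine encodes BA.5, and protocol 2.2 notes that authorized boosters moved to XBB.1.5 from 11 September 2023. SAP 4.4.1.1 plans binding IgG summaries against ten spike antigens, among them XBB.1.5 and XBB.1.16, so the sponsor is interested in breadth across variants. Where a participant's virus was sequenced, however, no planned output would show which variant it was or how its spike differs from the vaccine's.

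**Working it through.** There is no figure in the plan to reproduce, so the check sets the passages side by side.

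1. **Are the texts current?** Yes. The protocol is Amendment 3 (07 February 2024). The SAP is Amendment 2 (15 February 2024), written to align with it. Both sides of the conflict are in the body of these versions, not in a change log.

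2. **Is the objective still live in both?** Yes. Protocol Table 3 and SAP Table 1 carry the same objective and the same two endpoints. Table 3 has five tertiary objectives: binding IgG, cell-mediated response, infection incidence, spike sequence, and further characterization of the response. This is 1 of 5, and 2 of its 2 endpoints are affected.

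3. **Will data be generated?** Conditionally. Protocol Table 9 takes swabs from all enrolled participants at Day 1, Day 8 and Day 15 (72 + 42 = 114 planned). Section 8.4.4.2.2 adds swabs at suspected and convalescent COVID-19 visits. Sequencing follows only if the swab is positive and has enough material, and the comparison endpoint applies only where an isolate is available.

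4. **Which document must specify the analysis?** The SAP, by protocol 9.4.3.

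5. **Does another part of the SAP supply the output?** No.
   - 4.4.3 gives percentages with infection by N-protein seroconversion, RT-PCR or AESI report, with no breakdown by variant.
   - 4.6.1 lists participants by infection category (asymptomatic, COVID-19, severe COVID-19) and lists COVID-19 test results. Lineage and sequence are not mentioned.
   - 4.2.1.1 and 4.3.1.1 call for listings of COVID-19 cases, again without sequence content.
   - 4.8.1 allows late tertiary data to be analysed in annexes to the report. That clause is general and does not mention sequencing, whereas 4.4.4 is specific and unconditional, so the general clause does not displace it.

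6. **Is the departure recorded?** No, and the neighbouring endpoint shows how the sponsor records one. For symptomatic RT-PCR infection, protocol Table 3 counts screening, Day 1, Day 8, Day 15 and unscheduled visits. SAP Table 1 counts Day 8, Day 15 and unscheduled visits, and SAP 4.9 explains the difference. There the table was edited and the change logged. For the sequence objective, a larger change, the table is unedited and 4.9 is silent.

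Result: the objective is kept, sequencing is planned, the analysis is left to the SAP, and the SAP excludes reporting without giving a reason or recording the change.

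**The case against.** The best defence has four parts.

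- **Tertiary output was always conditional.** The SAP covers analyses for the clinical study report. Protocol 9.5.1 and SAP 4.8.1 promise at least the primary and secondary endpoints in the final report and only the available tertiary ones in the final analysis, with annexes for late data. This stands as a limit on the consequence. It does not remove the contradiction: data that may be sparse or late justify a conditional or delayed listing, not an unconditional statement that nothing will be reported. Neither document says the sequences will be reported elsewhere.
- **The SAP did not forget the endpoint.** It says openly what will happen to it. That is true, and it is why the smallest acceptable repair is to align Table 1 and add a reasoned entry in 4.9.
- **Nothing important depends on it.** Protocol 8.4.4.2.2 says efficacy will not be evaluated, all analyses are descriptive, and each dose group has 18 vaccine recipients per part. This stands in full.
- **Much of the information is already listed.** SAP 4.6.1 covers infection category and test results, so a separate new listing would largely duplicate it. This also stands, and the fix is framed accordingly.

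A reader might go further and infer that the infection percentages in SAP 4.4.3 cannot be interpreted without variant data. The documents do not support that. Those percentages remain valid as incidence. They also include cases found only by N-protein seroconversion at Day 15, Day 31 or Month 6, which have no positive swab to sequence, and no RT-PCR is scheduled after Day 15. Reporting sequences would not give a full variant breakdown of 4.4.3.

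**Conclusion.** The inconsistency is real and rests on wording alone, with no numerical assumption. Under the SAP as written, one descriptive tertiary objective, with both its endpoints, has no output, and the departure is neither explained nor recorded. No primary, secondary or safety result is affected. It is worth correcting because the correction is cheap and lets the trial answer a question it set itself.

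Two stronger readings should be resisted.

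- A reader might infer that the objective can never be answered. The documents support only that it has no output under the current SAP. Sequencing remains planned, and a revised SAP or an annex could still report it.
- A reader might try to put a number on the lost data. Assuming 5% to 20% of 114 participants were RT-PCR-positive gives 114 × 0.05 = 5.7 to 114 × 0.20 = 22.8, about 6 to 23. That range is an assumption with no source in the documents, and it counts positive participants, not sequences. Sequences also depend on the share of positives with enough material, which is not stated. The number of sequences is unknown and may be very small.

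**What to change.** Replace SAP 4.4.4 with a conditional listing. For each RT-PCR-positive participant with a sequence available, show the variant or lineage and the spike differences from the vaccine sequence. Add these as columns to the SARS-CoV-2 infection listing already planned in SAP 4.6.1, with arm, study part and study day displayed. Study day is needed because the Day 1 swab is taken before vaccination, so pre-vaccination positives must be separable from later ones. If the data arrive after the final analysis, use the annex route in SAP 4.8.1.

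Cost: SAP wording plus a small amount of data-transfer and programming work. The sequencing itself is already planned.

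If the sponsor will not report the data, align SAP Table 1 with 4.4.4 and record the change, with its reason, in SAP 4.9. That needs only a SAP edit. Removing the objective or the sequencing step from the protocol is a different matter: it would need a protocol amendment, and non-reporting in the study report does not by itself show that sequencing is unnecessary.

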# 4.5. Analysis Interpretation

All analyses are descriptive.

# 4.6. Other Safety Analysis

## 4.6.1. COVID-19 Assessment and COVID-19 AEs

A participant with an AE of SARS-CoV-2 infection can be categorized as "Asymptomatic SARS-CoV-2 infection", "COVID-19" or "Severe COVID-19" to the case diagnosis question from the COVID-19 coronavirus infection assessment electronic Case Report Form (eCRF).

Any case of "COVID-19" or "Severe COVID-19" is an AESI; and will be captured and described.

The listing of participants with any category of SARS-CoV-2 infection will be provided based on the Exposed Set.

The listing of participants who had a COVID-19 test performed with their results will be provided on the Exposed Set.

